3.0 Objectives

- Describe the study's purpose, specific aims, or objectives.
- State the hypotheses to be tested.

In this study, we will test our model for the purpose of delineating the extent to which OAA can bring value to patient care in VHA. We plan to control for demographic factors, namely: age, sex, race, health literacy, and internet access. The project will be conducted in primary care and one specialty clinic: diabetes. We select diabetes because of its high prevalence in Veterans, the presence of a specific marker of disease control (Hgb A1C), and that disease management now relies on a growing number of medications and dietary interventions that can be complex and overwhelming for patients. OAA, hence, may offer substantial benefits to patients and their caregivers and, if it does, the effect should be captured by falling Hgb A1c levels among those with baseline poor disease control. As noted, we also plan to study the impact of OAA on uncontrolled BP, but that data can be collected entirely in primary care given the very high prevalence rate.

This study has three aims, with the first two designed to test measurable hypotheses. The third is qualitative:

Aim 1: Assess the impact of an open access audio program on two behaviors (patient activation, treatment plan adherence), and two chronic condition measures (glycosylated hemoglobin, blood pressure). Secondary analysis will descriptively measure effect size on ED visits and hospital admissions.

Hypotheses:

- 1A: OAA increases patient activation.
- 1B: OAA increases care plan adherence, including fewer no-shows and more on-time refills.
- 1C: OAA reduces Hgb A1c and BP

Aim 2: Assess the impact of open access audio on provider communication behavior and on their attention to patient contextual factors (i.e. individual Veterans needs and circumstances relevant to planning effective care).

Hypotheses:

- 2A: Providers obtain higher scores on measures of communication behavior when they know they are being recorded.
- 2B: Providers obtain higher scores on measures of attention to patient contextual factors essential to care planning when they know they are being recorded.

Aim 3: Assess patient, provider, and leadership perceptions of the extent to which the program is safe, not burdensome, and worthwhile at both the start and at two years into the program.

- Indicate the relevance to Veterans and the VA

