just in the diabetes clinics where every patient has diabetes, many have an A1c>8, and A1c is re-checked at frequent intervals. Hence, analysis of an effect of OAA on diabetes control will occur only in the diabetes clinic population.

- All other measures to achieve Aim 1 will occur in analysis of data collected in both the diabetes and primary care clinics. Hence data on the effect of OAA on show-rates (visit adherence), medication refill rates, blood pressure control etc...will be pooled for patients randomized to Arms 1 and 2 in both the diabetes and primary care clinics.
- The PAM will be applied to the smallest possible subsample of Arms 1 and 2 to test hypothesis 1A (figure 2) with 80% power (Table 4.1, p 24) because it requires a phone call and takes about three minutes of RA and patient time. Subsamples will be drawn at random without replacement by computer. As shown in the Gantt chart (Table 2, p. 18), these calls will be spread out and administered 1-2 weeks post visit (Table 4.0, p 23). This is in contrast to measures of blood pressure, Hgb A1c, and visit and medication adherence, which are extracted from the data warehouse.
- Arm 3, essential to achieve Aim 2, will only occur exclusively in the primary care clinic because it requires blinding physicians to being audio recorded which is not relevant to measuring the effect of OAA on diabetes control, and would confound that measurement.
- Similar to PAM, the SEGUE and 4C analysis require RA time and effort, so will be applied to the smallest possible samples. Whereas PAM is intended to measure the effect of OAA (Arm 1) compared to control (Arm 2) on patient activation, SEGUE and 4C are intended to measure the effect of the physician knowing they are being recorded (Arm 2) versus not knowing (Arm 3) on the process (SEGUE) and content (4C) of the physician's decision making. The SEGUE checklist and the 4C coding occur while the RA is listening to the audio of a visit, randomly sampling 250 audios from the 827 primary care visit audios in Arm 2 for comparison with the 250 audios from Arm 3. Random sampling from Arm 2 primary care visits will be performed by computer without replacement and without regard to whether they are also part of the hypothesis 1A subsample.

Research activities for testing each aim: Anticipating and mitigating risks

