As summarized in Table 4, we will apply several measures to assess the effectiveness of the intervention, testing hypotheses to achieve Aims 1 and 2. For each hypothesis, comparisons between arms will be made using mixed-effect linear or logistic regression as appropriate for the outcome, with a fixed effect of study arm, VA site, and primary vs. secondary care setting, and a random effect of provider to accommodate clustering of visits within providers. Of primary interest is the direction, magnitude, and significance of the regression coefficient associated with study arm. Primary analysis will compare arms on an intention-to-treat basis, without regard to whether audio made available in Arm 1 is actually accessed by anyone; secondary analyses will include covariates representing whether, how often, and by whom (patient or provider) audio is actually accessed in Arm 1 to assess the impact of audio use (vs. availability). As patients will be randomized to arms, we do not expect demographic or other patient differences among arms, but will conduct tests for differences, and if any variables differ significantly among arms, we will include them as covariates in the regression models.

Table 4. Hypotheses and evaluation strategy for effectiveness of intervention (Aims 1 and 2)

Hypothesis	Evaluation Strategy
1A: OAA increases patient activation.	Administer PAM (Appendix A-1) 1-2 weeks post visit via phone call and compare scores in Arm 1 vs. Arm 2
1B: OAA increases care plan adherence, including fewer no-shows and more on-time refills.	Utilizing the data warehouse measure Return Visit Adherence (RVA) and refill rates (PDC) ^{24,32,33} in Arms 1 vs. 2.
1C: OAA reduces Hgb A1c and BP	Same as above: Utilizing data warehouse measure A1c and BP.
2A: Providers obtain higher scores on measures of communication behavior when they know they are being recorded.	Completed by trained RA off of Audio: SEGUE checklist for communication completed by research team (Appendix A-2) ²⁵ , comparing randomly sampled visits in Arm 2 vs Arm 3.
2B: Providers obtain higher scores on measures of attention to patient contextual factors essential to care planning when they know they are being recorded.	4C for contextualization of care ³⁴ , comparing randomly sampled visits in Arm 2 vs Arm 3.

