Table 4.2 lists the calculated power for the analyses for Hypothesis 2A and 2B (comparisons of Arm 2 vs. Arm 3) based on actual Veteran visits by outcome. Baseline SEGUE scores are based on SEGUE's validation study among general internists (mean 17.5, sd 1.77); that study found that medical students in a skills lab achieved mean SEGUE scores of 21.1 (sd 2.1), and we take that as our minimal expected level of improvement from knowledge that one is being observed. Baseline rates of contextual probing and planning are based on our prior study in the VA using recordings without provider awareness or patient access (as in Arm 3), and incorporate the expectation that contextual red flags suitable for probing will be present in 2/3 of encounters and contextual factors that should be incorporated in planning will be present in 1/4 of encounters overall.¹⁴ Expected increases in probing and planning are based on odds ratios from our prior study comparing these measures in undercover visits to providers with the same cases presented to medical students in a testing setting (and are thus conservative measures of how much better providers would likely perform if they were aware vs. unaware they were being tested).¹³ To obtain at least 80% power for each of these comparisons, we will randomly sample 250 primary care clinic visits (from 827 Arm 2 primary care visits), and enroll all 250 primary care visits in Arm 3 for the SEGUE and 4C coding processes. For 4C, we expect 168 visits/arm with red flags suitable for probing and 63 visits/arm with contextual factors suitable for planning.

Table 4.2: Expected differences and power for planned analyses for hypotheses 2A and 2B

Outcome	Baseline (doctor unaware, n=250)	Expected (doctor aware, n=250)	Sample size (total)	Power
SEGUE provider score	17.5	21	500	99%
Contextual probing rate ^{13,26}	32%	47%	500	80%
Contextual	59%	82%	500	82%

planning rate ^{13,26}				
--------------------------------	--	--	--	--

All effects measured in Aim 1 and 2 will be adjusted for patient sociodemographic characteristics which will be obtained from the CDW (including age, gender, and race) or from administering the REALM-SF to assess literacy. Internet access, for those in the intervention arm, will be ascertained by census track using geocoding of patient addresses, based on FCC data, a method developed by Perzynski et al.^{37,38}

Aim 3:

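### Section 5.6 gives two covariate rules for the Aim 1 and 2 models without saying which governs, and one of them chooses covariates by significance tests between randomized arms

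*Combined protocol and SAP*

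**What the plan says.** Three places in the combined protocol and SAP bear on the covariates.

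- **Section 5.6, paragraph before Table 4.** For each hypothesis the model is a mixed-effect linear or logistic regression "with a fixed effect of study arm, VA site, and primary vs. secondary care setting, and a random effect of provider". Because patients are randomized, no demographic or other patient differences are expected, but the team "will conduct tests for differences, and if any variables differ significantly among arms, we will include them as covariates in the regression models". No variable list and no significance level are given.
- **Section 5.6, after Table 4.2.** "All effects measured in Aim 1 and 2 will be adjusted for patient sociodemographic characteristics", with age, gender and race (from the data warehouse) and REALM-SF literacy named. There is no condition.
- **Section 3.0.** "We plan to control for demographic factors, namely: age, sex, race, health literacy, and internet access". This too is unconditional. On the last item, Section 5.6 adds: "Internet access, for those in the intervention arm, will be ascertained by census track using geocoding of patient addresses".

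Section 6.0 reports that a Data Analysis Plan was submitted to the DSMB and approved. It is not part of these documents.

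**The concern.** The arm coefficient is the quantity of primary interest, so the model that produces it should be fixed before outcomes are seen by arm. Here the same four patient variables are always in the model under one sentence, and in it only after a significant test under another.

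The testing rule is also weak in itself. In a randomized trial a significant difference between arms in a pre-treatment variable is a chance event. The test reacts to the size of that accident and not to whether the variable predicts the outcome, and prediction is what makes adjustment worthwhile. For the logistic outcomes, the covariate set also determines which conditional odds ratio is estimated.

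Internet access raises a smaller problem of the same kind: a variable recorded in one arm only cannot adjust a comparison between arms.

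**Working it through.** No sample size, power or alpha in the plan depends on the covariate rule, so there is no stated figure to reproduce. The check is a comparison of texts and three calculations.

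**1. Do the rules differ for the same variables?** Both apply to all Aim 1 and 2 hypotheses. The testing rule covers demographic or other patient variables; the unconditional rule covers age, gender, race and literacy. Age, gender and race therefore fall under both by name, and literacy does as a patient variable. Neither sentence refers to the other, and neither is labelled primary or sensitivity.

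**2. How often would the two rules give different models?** This matters only if the testing rule governs the four named variables. Assume independent tests, one per variable. The plan gives no level.

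- 5% level: P(none selected) = 0.95^4 = 0.815, or 81%
- 1% level: 0.99^4 = 0.961
- 10% level: 0.90^4 = 0.656

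If the tests are correlated at 0.5, simulation gives 0.844, 0.965 and 0.712. The unconditional rule always includes all four.

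**3. What does test selection cost?** Take a linear model with 462 per arm (half of the 924 PAM calls), four independent covariates that together explain a share R-squared of the outcome variance, and an effect for which the unadjusted test has 80% power (standardized effect 1.960 + 0.842 = 2.802). Fixed adjustment divides the standard error by 1/sqrt(1 − R-squared), so power is Φ(2.802/sqrt(1 − R-squared) − 1.960):

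- R-squared 0.1: Φ(2.953 − 1.960) = 84.0%
- R-squared 0.2: Φ(3.132 − 1.960) = 87.9%
- R-squared 0.4: Φ(3.617 − 1.960) = 95.1%

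Simulation (6,000 replicates per scenario, selection at 5%) gives:

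| R-squared (assumed) | Power, no covariates | Power, fixed set | Power, test-selected | Type I error, fixed set | Type I error, test-selected |
|---|---|---|---|---|---|
| 0.1 | 80.1% | 83.9% | 80.4% | 0.051 | 0.050 |
| 0.2 | 79.9% | 87.9% | 81.0% | 0.049 | 0.047 |
| 0.4 | 80.2% | 95.2% | 82.2% | 0.049 | 0.039 |

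The Monte Carlo standard error is about sqrt(0.8 × 0.2/6000) = 0.5 percentage points for power and sqrt(0.05 × 0.95/6000) = 0.003 for type I error. The fixed set matches the formula. Test selection recovers little of the gain and becomes slightly conservative as R-squared rises.

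**4. Does the covariate set move the odds ratio?** Section 5.6 expects an odds ratio of 0.5 for the 1B outcomes. For blood pressure, Table 4.1 implies (0.24/0.76)/(0.39/0.61) = 0.494. Neither is described as conditional on covariates or not. As an illustration, take 0.50 as conditional on a normal covariate score with SD s on the logit scale, ignore the provider effect, and average over the score:

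- Arm 2 rate 39% (blood pressure): 0.505, 0.517 and 0.559 for s = 0.25, 0.5 and 1.0
- Arm 2 rate 7% (no-show): 0.501, 0.505 and 0.521

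These figures compare no covariates with all of them; a partly selected set would shift less.

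**5. Internet access.** Only Arm 1 is ascertained, so the variable is absent for all 1,029 Arm 2 patients among the 2,058 in the Aim 1 comparison, and for both arms of the Arm 2 versus 3 comparison.

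**The case against.** The best defence is that the sentences fit together: Sections 3.0 and 5.6 agree on a fixed core of age, sex, race and literacy, and the testing rule only adds other variables that turn out imbalanced. That reading is available, and under it the 81% figure has no application. But the testing sentence names demographics among the differences it covers, which would be redundant if they were always included. The defence also leaves the testing rule in place for the additional variables, where it has the same weakness.

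A second defence is that the harm is small. This largely stands. A reader might infer that choosing covariates this way biases the treatment comparison or inflates false positives. Randomization protects the comparison, and the simulated type I error never rose above nominal. The loss is relative to fixed adjustment only; the plan's power figures do not state any gain from covariates.

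A reader might also infer a material distortion of the odds ratios. At s of 0.5 or less the shift is at most from 0.50 to 0.517. The larger value needs a strongly predictive score, and the documents give no value of s.

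A reader might further think the care-setting term breaks some models, since "analysis of an effect of OAA on diabetes control will occur only in the diabetes clinic population" and "Arm 3, essential to achieve Aim 2, will only occur exclusively in the primary care clinic". A factor with one level simply drops out and no estimate changes; the wording only needs tidying.

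Finally, the approved Data Analysis Plan may already contain the variable list and the rule. The most that can be said is that this document does not settle them. For internet access, use only within the Arm 1 audio-use analyses is a plausible intention, but Section 3.0 does not say so.

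**Conclusion.** The concern holds in a limited form. Section 5.6 contains a conditional and an unconditional covariate rule for the same models and does not say which governs. Whichever reading is taken, selecting covariates by tests between randomized arms is inferior to a fixed set: the primary model depends on the data, prognostic value is ignored, and for logistic outcomes the conditional odds ratio being estimated is not fixed in advance.

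The cost is lost precision. Under the linear simulation it is about 3 to 13 percentage points of power against fixed adjustment (83.9 − 80.4 = 3.5; 95.2 − 82.2 = 13.0). That range rests entirely on the assumed R-squared values of 0.1 to 0.4, which the documents do not supply. The 81% chance of selecting none of the four named variables holds only if the testing rule governs them, with independent tests at an assumed 5% level. The documents do not support a claim of bias or type I error inflation.

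The internet-access point is secondary: as written, the variable cannot adjust any planned comparison between arms.

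**What to change.** - Delete the sentence in Section 5.6 that adds covariates by significance tests. Report baseline characteristics by arm descriptively.
- State one prespecified primary set for Aims 1 and 2: age, sex, race, REALM-SF, site, care setting where both clinics contribute (so not for A1c or Aim 2), and the provider random effect.
- Make this agree with the Data Analysis Plan cited in Section 6.0, and settle it before outcomes are compared by arm.
- For internet access, state that it is used only in the Arm 1 audio-use analyses and remove it from the Section 3.0 list. Alternatively, geocode Arm 2 by the method already planned and use it in the Aim 1 models.

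The main change is wording only, because every variable in the set is already planned for all arms. Limiting internet access to Arm 1 is also wording; geocoding Arm 2 would add an address lookup for 1,029 patients.

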We have designed a three arm RCT (figure 2, below), with each arm varying as to who gets access to the audio after the visit and who is aware of the fact that audio recording is occurring during the visit. The design establishes the conditions for achieving the first two aims of the study, with each aim framed as testable hypotheses. Arm 1 is the intervention, with both provider and patient aware of the recording. It is designed to represent how OAA would be utilized in actual practice. In Arm 2 all parties are also aware of the audio recording, but this time neither gets access to the audio after the visit (although the research team does). Arm 2 is a control for isolating the effect of patient access after the visit to the audio in Arm 1. Both patient and physician are blind to whether they are in Arm 1 or 2 until after the visit. Comparing these two arms will achieve the first aim of the study. Arm 3 is a second kind of control, as the audio is again not shared with the patient. In this arm, however, the patient conceals the audio recorder, typically in an accessory such as an eye glass case (a method we have employed extensively¹⁴), so that the provider is unaware they are being audio recorded until after the visit, enabling the research team to achieve the second aim of the study by comparing Arm 3 to Arm 2, isolating the effect of being aware they are being audio recorded on the provider's interactions with the patient. Whereas in Arm 3 the physician is unaware they are being recorded, in Arms 1+2, they are aware and also know there is a 50% chance the patient will have access to the audio. This design enables Arm 2 to serve both as a control for Arm 1 to achieve Aim 1 (since patient only gains access to the audio in Arm 1) and as comparator with Arm 3 – to achieve Aim 2 -- since the physician believes the patient may gain access to the audio.

[figure not shown]
Figure 2: Study Design

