7.0 Privacy and Confidentiality

- Describe whether the study will use or disclose subjects' Protected Health Information (PHI).

Patient PHI: The study will be collecting PHI, consisting of audio recordings of encounters and patient email addresses, to send them links to their audio files. As noted above, the data analyst will extract the patient outcomes and demographic data from the Central Data Warehouse. He will have access to PHI briefly as he runs search in the Corporate Data Warehouse.

For data tracking purposes, we will create a master spreadsheet with a row for each patient encounter. A code will be assigned to each encounter linked to a cross-walk file (see below).

The three patient surveys (literacy survey, exit survey, and patient activation measure) will be handled similarly: they will be assigned an encounter specific code, with a link to the cross-walk file.

Provider Subject PHI: Survey and focus group data is not PHI. However it is possible that during an employee focus group discussion about the OAA project, that a clinician could mention a patient's name or other identifier. This is not likely as the topic of the focus groups is the OAA project not the care of any specific individual.

- Describe the steps that will be taken to secure the data (e.g., training, authorization of access, password protection, encryption, physical controls, Certificates of Confidentiality, and separation of identifiers and data)

The data encryption and storage methods are highly secure, but are monitored for safety using standard software storage review processes, including log analysis.

All study team members will be required to maintain necessary research training, and the PI of the study team will oversee completion and maintenance of any required training.

The cross-walk file will be kept in a separate file from the master file, accessible only with permission from the PI with access enabled by the IT data manager. Access is based exclusively on need, as follows: The data analyst who access the CDW to look up A1c and BP, RVA and PDC; The RA who completes the PAM 1-2 weeks post visit; and the RA who completes the SEGUE and completes the 4C coding, both off the audio.

The research records and data will be stored and destroyed in compliance with record Control Schedule (RCS) 10-1.

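### Always including the pre-visit A1c or BP in the hypothesis 1C models, instead of only after a significant imbalance test, is a nearly free gain in precision

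*Combined protocol and SAP*

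**What the plan says.** Section 5.6 (Data Analysis) specifies "mixed-effect linear or logistic regression as appropriate for the outcome". The terms that are always in that model are given as follows: "with a fixed effect of study arm, VA site, and primary vs. secondary care setting, and a random effect of provider". The section then says that patient differences between arms are not expected but will be tested, and "if any variables differ significantly among arms, we will include them as covariates in the regression models".

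Two other statements make some covariates unconditional. Section 3.0 (Objectives) says "We plan to control for demographic factors, namely: age, sex, race, health literacy, and internet access". After Table 4.2, section 5.6 says "All effects measured in Aim 1 and 2 will be adjusted for patient sociodemographic characteristics", naming age, gender, race and literacy. Neither mentions the patient's A1c or blood pressure before the visit.

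The values should be within reach. Section 7.0 gives crosswalk access to "The data analyst who access the CDW to look up A1c and BP, RVA and PDC". Section 5.1 describes the diabetes clinics as places where "many have an A1c>8, and A1c is re-checked at frequent intervals". It also states: "Both patient and physician are blind to whether they are in Arm 1 or 2 until after the visit". A value recorded on or before the index visit therefore cannot have been affected by access to the audio.

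**The concern.** In a randomised comparison, a covariate earns its place by predicting the outcome, not by happening to differ between arms. The previous A1c or blood pressure is likely to be a good predictor of the repeat value. The plan decides on its inclusion by a test that, under randomisation, is significant only by chance. In roughly 19 trials of 20 the value is left out and its variation stays in the error term. The final model also depends on the data.

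At stake is efficiency, mainly for A1c, which has the smallest sample of the Aim 1 outcomes (404, against 924 for patient activation and 2058 for the others).

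**Working it through.** **Inputs from the documents.** A1c: 202 per arm, 66-70% against 33-35% (midpoints 68% and 34%). BP: 1029 per arm, 39% against 24% (Table 4.1 and the text above it). Target power is at least 80%.

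**Assumptions.** Two-sided 5% for both the outcome test and the imbalance test. Correlation r between pre-visit and repeat value, after the planned covariates, of 0.3, 0.5 or 0.7. Full planned samples, no missing repeats, no provider clustering. None of these is given in the documents.

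**1. Power at the plan's own effects, unadjusted.** Power = Φ[(p₂ − p₁ − 1.96·SE₀)/SE₁], with SE₀ pooled and SE₁ unpooled.
- A1c: SE₀ = √(2 × 0.51 × 0.49/202) = 0.0497; SE₁ = √((0.68 × 0.32 + 0.34 × 0.66)/202) = 0.0468. (0.34 − 1.96 × 0.0497)/0.0468 ≈ 5.2, so power exceeds 99.9%. The printed 80% does not reproduce. That is a separate matter and is not relied on here.
- BP: SE₀ = 0.0205, SE₁ = 0.0202. (0.15 − 1.96 × 0.0205)/0.0202 ≈ 5.4, so power exceeds 99.9%, consistent with the printed 99%.

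At these effects adjustment has nothing to add.

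**2. A smaller effect, linear model on the follow-up value, A1c.** The difference detectable with 80% power unadjusted is 2.80 × √(2/202) = 0.279 SD. Adjustment multiplies the standard error by √(1 − r²) and is worth 1/(1 − r²) times the patients.

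| r | SE ratio | SE cut | Equivalent sample | Detectable difference (SD) |
|---|---|---|---|---|
| 0.3 | 0.954 | 5% | ×1.10 | 0.266 |
| 0.5 | 0.866 | 13% | ×1.33 | 0.241 |
| 0.7 | 0.714 | 29% | ×1.96 | 0.199 |

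Simulated power at 0.279 SD (10,000 runs per r):

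| r | Never adjust | Test first | Always adjust |
|---|---|---|---|
| 0.3 | 79.1% | 79.7% | 83.0% |
| 0.5 | 80.0% | 81.0% | 89.9% |
| 0.7 | 80.1% | 82.0% | 97.7% |

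The baseline value entered under test-first in about 5% of runs. At r = 0.5 the available gain is 89.9 − 80.0 = 9.9 points, and test-first keeps 81.0 − 80.0 = 1.0 of them. With no true effect, test-first rejected in 5.1%, 4.2% and 3.4% of runs, so there is no inflation.

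**3. Threshold outcome, logistic model.** Drops with about 80% unadjusted power were used: A1c 68% to 54.5% (6,000 runs per r), BP 39% to 33.1% (2,500 runs per r, one latent baseline score).

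| r | A1c test first | A1c always | BP test first | BP always |
|---|---|---|---|---|
| 0.3 | 80.3% | 82.6% | 80.7% | 82.7% |
| 0.5 | 81.0% | 86.9% | 81.2% | 86.0% |
| 0.7 | 81.0% | 93.0% | 82.1% | 93.5% |

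Here the gain comes from a larger conditional log odds ratio, not a smaller standard error. For A1c the mean log odds ratio moves from −0.58 (SE 0.207) to −0.61, −0.69 and −0.86 (SE 0.214, 0.228, 0.258).

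**4. A1c analysis limited to poor control at baseline.** Keeping the top 68% of a normal baseline leaves 0.477 of its variance. With r′ = r√0.477/√(1 − r² + 0.477r²), r of 0.3, 0.5 and 0.7 becomes 0.21, 0.37 and 0.56. The SE cut falls to 2%, 7% and 17%. A comparison with 80% power unadjusted in that subset rises to about 82%, 85% and 92%.

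**The case against.** The strongest objection is that the plan loses nothing at its own effects. Every gain above needs a smaller effect that the documents do not contain. That stands, and it makes this an efficiency suggestion rather than a defect.

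Second, baseline may already be used in another way. Section 3.0 expects falling A1c among patients with poor control at baseline, and section 5.6 describes patients who have both poor control and a repeat measurement. This could mean a restricted analysis or a change from baseline. The totals of 404 and 2058 in Table 4.1 point to the full sample, but the text is not decisive. Under restriction the gain is smaller (step 4). For a change outcome, adding the baseline would still cut the standard error, by about 19%, 13% and 8% at r of 0.3, 0.5 and 0.7. The gain stays positive under each reading, but the 83% to 98% range belongs only to the full-sample, follow-up-value reading.

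Third, the simulations leave out provider clustering and missing values, and the BP case uses one baseline score where the fix names two. These affect the size of the gain, not its direction.

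Fourth, section 6.0 mentions a Data Analysis Plan approved by the data safety monitoring board. It is not among the documents and may already settle the matter. That would not change what section 5.6 says.

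A reader might infer that testing first throws away almost all of the trial's power, or that it invalidates the 1C tests. Neither is supported. Power under the rule stays at 80% to 82% in the illustration; what is forgone is most of the extra gain. Type I error is at or slightly below the nominal level.

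**Conclusion.** The point holds as a cheap improvement. As a covariate, pre-visit A1c or BP can reach the 1C models only through a significance test of imbalance, and that rule forfeits most of the precision the value could supply. For A1c at 202 per arm, with an effect giving about 80% unadjusted power, the difference is about 83% to 98% against 80% to 82% on the linear scale, and about 83% to 93% against 80% to 81% on the threshold scale. These figures rest on the assumed r and on complete, unclustered data. The gain is lower if the analysis is restricted to poor control at baseline.

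The 80% printed for A1c in Table 4.1 might suggest that this comparison is already marginal at the planned effect. It is not: the printed rates and sample give power above 99.9%. The case for the change is insurance against a smaller true effect.

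**What to change.** In section 5.6, state that each hypothesis 1C model includes, as a fixed covariate, the patient's most recent data-warehouse value on or before the index visit: A1c for the A1c outcome, systolic and diastolic pressure for the BP outcome. This should apply whatever any test of imbalance shows. State in advance how a missing pre-visit value is handled. Sample size and outcomes do not change. If the approved Data Analysis Plan already fixes baseline adjustment, align section 5.6 with it.

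The cost is a wording change and one more A1c, or one systolic/diastolic pair, per patient from a source the analyst already queries. The one real drawback is that in a logistic model the odds ratio becomes conditional on baseline and is no longer directly comparable with the rates in Table 4.1. A standardised risk difference should be reported beside it.
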